10.2 Concentration and PK Parameter Summary Tables

Summary statistics (i.e. n, mean, SD, CV%, median, minimum, maximum, geometric mean, geometric SD and geometric CV%) of concentration data will be calculated for the following analytes/matrices. The number of BLQ values (n) per time point will also be presented. Geometric statistics will not be calculated for pre-dose concentrations.

- Whole blood concentrations of rencofilstat by time point
- Plasma concentrations of total radioactivity by time point
- Whole blood concentrations of total radioactivity by time point
- Whole blood:plasma concentration ratios of total radioactivity by time point

Summary statistics (i.e. n, mean, SD, CV%, median, minimum and maximum) of whole blood PK parameters will be calculated for rencofilstat and total radioactivity. Geometric mean, geometric SD and geometric CV% will be presented for all PK parameters except Tlag and Tmax.

Non-measurable values reported in the concentration data (i.e., values that are BLQ), will be entered as zero for the determination of summary statistics with the exception of geometric means, geometric SD and geometric CV%, where BLQ values will be imputed as half the LLOQ value. This also applies to any concentrations that are defined as PK parameters (e.g., C24). Data recorded as NR, NS or NC will be handled as missing (i.e., no assumption will be made about the actual concentration).

10.3 Concentration and PK Figures

Mean, spaghetti and individual whole blood and plasma concentration vs time plots will be produced on both the linear/linear scale and on log10/linear scale. For all plots on a linear/linear scale, post-dose concentration values reported as BLQ will be set to zero, up to the point at which all concentrations fall below BLQ, after which they will be presented as missing. For all plots on a log 10/linear scale, post-dose concentration values reported as BLQ will be set to half the BLQ value, up to the point at which all concentrations fall below BLQ, after which they will be presented as missing. Where curves from multiple treatment regimens or subjects are overlaid on the same plot, symbols will be used to identify different subjects/ treatment regimens and a legend will be included on the plots to define the symbols used.

Mean concentration vs time plots (using nominal times) will be produced for:

- Rencofilstat in whole blood and total radioactivity in plasma and whole blood, on the same plot (3 profiles per plot)
- Rencofilstat in whole blood and total radioactivity in whole blood on the same plot (2 profiles per plot)
- Total radioactivity in plasma and whole blood on the same plot (2 profiles per plot)

These will be produced as follows:

- Linear/linear scale using arithmetic mean concentrations (error bars ± arithmetic SD)
- Log10/linear scale using geometric mean concentrations (error bars x/÷ geometric SD)

Separate spaghetti plots (using actual sampling time after dosing) will be produced for each matrix and analyte with each plot displaying 1 line per subject.

Individual plots (using actual sampling times after dosing) will be produced separately for each individual subject with all analytes and matrices on the same plot.

10.4 Concentration and PK Listings

The sample collection data (e.g. collection times) for PK samples will be listed. In addition, all concentration data and PK parameters will be listed on a per subject basis. Any flags used will be included as a footnote with the appropriate definition.

10.5 Statistical Analysis of PK Parameters

No formal statistical analysis will be performed for the PK data in this study. Descriptive statistics (i.e. n, mean, SD, median, CV%, minimum and maximum) are considered adequate for a study of this type.

11 Safety Assessments

Safety data summaries will be presented overall and the safety analysis set will be used throughout.

11.1 Extent of Exposure and Treatment Compliance

The total dose given (including the dose of radioactivity in microcurie [μ Ci] and megabequerel [MBq]) will be summarised (i.e., n, mean, SD, median, minimum and maximum) for rencofilstat.

Dosing details (including the date and time of all IMP administrations and any comments) will be listed for all enrolled subjects. Any recorded deviations from the planned dosing regimen will be listed as protocol deviations.

11.2 Adverse Events

Throughout the study, all AEs will be evaluated by the investigator and noted in the AE section of the eCRF study build specification. An AE is any untoward medical occurrence in a subject that occurs either before dosing (referred to as a pre-dose AE) or once a medicinal product has been administered, including occurrences which are not necessarily caused by or related to that product.

AEs will be coded using MedDRA v26.0 (or more recent version), including PT and SOC.

AEs will be classified into the following categories:

- Pre-dose AEs: AEs recorded at screening or with a start date and time prior to the first dose of IMP
- Treatment -emergent AEs (TEAEs): AEs that commence during/after the first dose of IMP or commence before first dose of IMP (i.e., a pre-dose AE or existing medical condition) but worsen in intensity during exposure to IMP

AEs will be classified as "mild," "moderate" or "severe" when considering their severity.

AEs will be classified as "unrelated", "possibly related" or "related" when considering their relationship to IMP. TEAEs classified as "possibly related" and "related" will be defined as adverse drug reactions (ADRs). An ADR is any AE where a causal relationship with the IMP is at least a reasonable possibility i.e., "possibly related" and "related". Pre-dose AEs will always have the classification of "unrelated".

If the severity or relationship to IMP of a TEAE is missing, the severity/relationship will be tabulated as "missing" in the summary tables.

When summary presentation is made by maximum severity, "missing" will be handled as follows:

- If there are other events (i.e. same SOC and PT code) with a maximum severity recorded as "moderate" or "severe" for that subject, then the maximum observed severity for that subject will be categorised and presented as "moderate" or "severe", respectively
- If there are other events (i.e. same SOP and PT code) with a maximum severity recorded as "mild" for that subject, then the maximum observed severity for that subject will be categorised and presented as "missing"

When summaries are presented by relationship to IMP, "missing" will be handled as follows:

- If there are other events (i.e. same SOC and PT code) with a most closely related association recorded as "possibly related" or "related" for that subject, then the maximum observed relationship for that subject will be categorised and presented as "possibly related" or "related", respectively
- If there are other events (i.e. same SOP and PT code) with a most closely related association recorded as "unrelated" for that subject, then the maximum observed relationship for that subject will be categorised and presented as "missing"

Where the start date of an AE is missing and the stop date is on or after the day of first dose of IMP or both the start and stop dates are missing then a "worst-case" scenario will be assumed i.e., the AE is assumed to have occurred post-dose and is therefore considered treatment-emergent. If a partial start date/time is available then the event will be considered as treatment-emergent unless the partial information suggests otherwise.

11.2.1 Summary Tables for Adverse Events

All pre-dose AEs (as defined in Section 11.2) will be excluded from the summary tables but will be listed for all enrolled subjects.

Descriptive statistical methods will be used to summarise the TEAE data.

The number and percentage of subjects reporting each TEAE will be presented for both SOC and PT. For summaries by SOC and PT, with the exception of TEAEs by severity and relationship to IMP, the number of subjects and the number of events will be summarised. For summaries by severity and relationship only the number of subjects will be summarised.

For counts of subjects experiencing events the following will apply:

- A subject with a TEAE in more than one body system will be counted once in the total number of subjects with TEAEs
- A subject with more than 1 TEAE in the same SOC counts only once at the SOC level
- A subject with more than 1 TEAE in the same PT counts only once at the PT level

For event counts, all events are included.

When it is necessary to calculate percentages, the denominator will be the total number of subjects in the safety analysis set and the numerator will be the total number of subjects reporting a TEAE within the relevant category.

Summaries presented for SOC and PT will be presented in descending order of frequency overall i.e., most frequently reported SOC in the study and then by most frequently reported PT in the study within each SOC.

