14.3 Recording Adverse Events

AEs (including SAEs) will be recorded from the time of providing written informed consent until discharge from the study. During each study visit the subject will be questioned directly regarding the occurrence of any adverse medical event according to the schedule in the source. All AEs, whether ascribed to study procedures or not, will be documented immediately in the subject's source. This will include the date and time of onset, a description of the AE, severity, seriousness, duration, actions taken, outcome and an investigator's current opinion on the relationship between the study drug and the event. A diagnosis and final opinion on the relationship between the study drug and the event will be provided at the end of the study by the investigator.

Any subject who withdraws from the study due to an AE will be followed up until the outcome is determined and written reports are provided by the investigator.

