11.2.1.2 Summary of Treatment-Emergent Adverse Events

All subjects reporting TEAEs will be summarised. Counts will be given for number of subjects and number of events. Subjects experiencing more than 1 TEAE will be counted only once for number of subjects but will be counted more than once for number of events.

Additionally, subjects reporting TEAEs will be summarised for SOC and PT. Counts will be given for number of subjects and number of events. Subjects experiencing more than 1 episode of a TEAE will be counted only once within each SOC and PT.

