11.2.2 Listings for Adverse Events

All pre-dose AEs (as defined in Section 11.2) will be listed including SOC and PT.

A separate data listing of all TEAEs will be provided including the SOC and PT. In addition, a listing of all SAEs will be provided.

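### SAP 11.2 and 11.2.1 give conflicting rules for an adverse event that starts before dosing and worsens afterwards

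*SAP*

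**What the plan says.** SAP 11.2 sorts adverse events into two categories. The first is defined by timing of onset: "Pre-dose AEs: AEs recorded at screening or with a start date and time prior to the first dose of IMP". The second, TEAEs, has two limbs. One covers events that begin at or after dosing. The other covers events that "commence before first dose of IMP (i.e., a pre-dose AE or existing medical condition) but worsen in intensity during exposure to IMP".

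Two rules then act on the first category:

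- **Tables (SAP 11.2.1):** "All pre-dose AEs (as defined in Section 11.2) will be excluded from the summary tables but will be listed for all enrolled subjects".
- **Causality (SAP 11.2):** "Pre-dose AEs will always have the classification of" unrelated.

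Other rules act on the second category or on events in general:

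- **TEAE tables (SAP 11.2.1.2):** "All subjects reporting TEAEs will be summarised".
- **TEAE listing (SAP 11.2.2):** "A separate data listing of all TEAEs will be provided including the SOC and PT".
- **ADRs (SAP 11.2):** these are TEAEs judged possibly related or related. The SAP adds: "An ADR is any AE where a causal relationship with the IMP is at least a reasonable possibility".
- **Investigator's opinion (protocol 14.3):** causality is for the investigator to give, in a sentence that reads, up to its last two words: "A diagnosis and final opinion on the relationship between the study drug and the event will be provided at the end of the study by". No exception is made for events that began before dosing.

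**The concern.** The SAP itself names a pre-dose AE as something that can become a TEAE, so the two categories are not mutually exclusive. A programmer holding an event that started before dosing and worsened afterwards has one rule to leave it out of the tables and another to put it in, with nothing to say which governs. The causality rule raises a second question: the SAP can assign a relationship that differs from the one the investigator gave.

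AE incidence is part of a secondary safety endpoint in a descriptive study. Where the exclusion or the fixed label makes a difference, it works in one direction only, towards fewer TEAEs or fewer ADRs. It also sits oddly beside the SAP's own approach to unknown dates. In SAP 11.2, an event with a missing start date that ends on or after the dosing day, or that has no dates at all, is taken as treatment-emergent on worst-case grounds. An event known to have worsened on drug could therefore be handled less conservatively than one whose dates are unknown.

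**Working it through.** The documents give no figure on this point, so there is nothing to reproduce. The check is to pass one event through each rule.

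**Does the overlap exist?** Take an AE that starts between consent and dosing, is still present at dosing, and worsens afterwards.

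1. Its start precedes the first dose, so it meets the pre-dose definition. That definition has no exception for later worsening.
2. It began before dosing and worsened during exposure, so it meets the second TEAE limb, which names pre-dose AEs explicitly.
3. It therefore carries both labels.

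**Which rules apply to it?** The exclusion in SAP 11.2.1 covers all pre-dose AEs and points back to the definition in 11.2, so it brings in that definition unqualified. The fixed-causality sentence is likewise unconditional. The requirement in SAP 11.2.1.2 to summarise all TEAEs is also unconditional. Exclusion and inclusion cannot both be followed.

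**What can the tables show?** Inputs and assumptions:

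- Planned enrolment is 6 (protocol 8.1; SAP 5.1), and all six are assumed to be in the safety analysis set, which is the percentage denominator (SAP 11.2.1).
- One subject has one worsened event and no other TEAE at the level tabulated. SAP 11.2.1 counts a subject once in the total, once per SOC and once per PT.
- The investigator judges the worsened episode possibly related.

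Incidence is the number of subjects with an event divided by 6, and 1/6 = 16.7%.

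| Reading | TEAE tables | ADR table |
|---|---|---|
| A. Exclusion of pre-dose AEs governs | 0/6 = 0% | 0/6 = 0% |
| B. TEAE rule governs the tables, but the event keeps its pre-dose label | 1/6 = 16.7%, shown as unrelated | 0/6 = 0% |
| C. Worsening removes the pre-dose label for every purpose | 1/6 = 16.7% | 1/6 = 16.7% |
| D. Worsening is recorded as a new AE with post-dose onset | 1/6 = 16.7% | 1/6 = 16.7% |

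The gap between A and the other readings in the TEAE tables is 16.7 − 0 = 16.7 percentage points. For ADRs the gap lies between A or B and C or D, and is also 16.7 points, given the assumed causality opinion. If the subject already has another TEAE in the same row, the subject percentage does not move. The event count still changes by one where events are counted, because SAP 11.2.1 includes every event in those counts.

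**How likely is it?** The documents give no frequency. AEs are collected from consent (protocol 14.1 and 14.3), and screening runs from Day -28 to Day -2. The event must also persist to dosing in a healthy volunteer whose ongoing eligibility is re-checked at admission or pre-dose (protocol 10.2), and must then worsen.

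**The case against.** The best defence is reading C. The second TEAE limb would serve no purpose if SAP 11.2.1 took the same events out again, so the sensible interpretation is that worsening turns the event into a TEAE, and that the exclusion reaches only what remains. SAP 11.2.1.2 and 11.2.2 support this by requiring every TEAE to be summarised and listed. On that reading the fixed unrelated label falls away too, and the investigator's opinion stands.

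This is probably what the authors meant, and it rules out the stronger claim a reader might infer, that worsened events necessarily disappear from the safety summaries. That is reading A only. Nor do the two effects add up. If the event is excluded, its causality label has no effect on the tables; if it is kept, it has not been lost. Individual pre-dose AEs, TEAEs and SAEs are all listed (SAP 11.2.2), so such an event can still be found.

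A reader might also infer from the second TEAE limb that a worsening must stay on the original AE record. The documents do not settle this. The limb does speak of an event that began before dosing, but it also covers an existing medical condition, which is collected as medical history (SAP 7.6) and need not have an earlier AE record. If the practice is to open a new AE at the time of worsening, the first limb applies and the conflict does not arise. Neither document states that practice.

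What the defence does not achieve is to resolve the text. The exclusion refers back to an unqualified definition, the causality sentence says always, and no precedence rule is stated. Reading C has to be supplied by the reader.

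**Conclusion.** The point holds as a conflict between stated rules. For a pre-dose AE that worsens, the SAP requires both exclusion from the summary tables and inclusion in them. Applied literally, the exclusion removes it from the TEAE tables. While it is still classed as pre-dose, it cannot be an ADR even if tabulated, whatever relationship the investigator assigns.

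With six subjects, one such event moves TEAE incidence by 16.7 percentage points. That rests on a safety set of six and on the subject having no other TEAE at the level shown. The ADR effect further requires a causality opinion of possibly related or related. The whole point requires that worsening is not recorded as a new post-dose event.

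The importance is low. Safety is a secondary, descriptive objective, the individual events stay in the listings, and no such event may occur. The clarification is desirable rather than essential.

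**What to change.** Make two wording changes in the SAP:

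1. In 11.2.1, exclude from the summary tables only those pre-dose AEs that do not worsen after dosing.
2. In 11.2, confine the automatic unrelated label to the same events, and state that a worsened episode takes the investigator's causality assessment, as any other TEAE does.

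One further sentence would help: whether a worsening is entered as a new AE with its own onset or as a change to the existing record.

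The cost is two phrases and, if adopted, that sentence. No new data, tables or listings are needed. The change is best made before database lock, when the protocol requires the analysis plan to be signed off (protocol 15.4).

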11.2.1.1 Overall Summary of Adverse Events

The following will be summarised for the safety analysis set:

- Number and percentage of subjects reporting at least 1 TEAE
- Number and percentage of subjects reporting severe TEAEs
- Number and percentage of subjects reporting ADRs
- Number and percentage of subjects reporting serious TEAEs
- Number and percentage of subjects reporting TEAEs leading to subject withdrawal
- Number and percentage of subjects reporting TEAEs leading to death
- Total number of TEAEs
- Total number of severe TEAEs
- Total number of ADRs
- Total number of serious TEAEs
- Total number of TEAEs leading to subject withdrawal
- Total number of TEAEs leading to death

11.2.1.2 Summary of Treatment-Emergent Adverse Events

All subjects reporting TEAEs will be summarised. Counts will be given for number of subjects and number of events. Subjects experiencing more than 1 TEAE will be counted only once for number of subjects but will be counted more than once for number of events.

Additionally, subjects reporting TEAEs will be summarised for SOC and PT. Counts will be given for number of subjects and number of events. Subjects experiencing more than 1 episode of a TEAE will be counted only once within each SOC and PT.

11.2.1.3 Summary of Treatment -Emergent Adverse Events by Severity

All subjects reporting TEAEs will be summarised by severity (i.e., mild, moderate or severe). Counts will be given for number of subjects, not number of events. Counts will be given by maximum severity (i.e., subjects experiencing more than 1 TEAE will be counted only once using the most severe episode).

Additionally, subjects reporting TEAEs will be summarised for SOC and PT by maximum severity (i.e., mild, moderate or severe). Counts will be given for total number of subjects, not for events. Counts by maximum severity will be given (i.e., subjects experiencing more than 1 TEAE will be counted only once within each SOC and PT using the most severe episode).

11.2.1.4 Summary of Treatment -Emergent Adverse Events by Relationship to IMP

All subjects reporting TEAEs will be summarised by relationship to IMP (i.e., unrelated, possibly related or related). Counts will be given for number of subjects, not number of events. Counts will be given by the closest relationship to IMP (i.e., subjects experiencing more than 1 TEAE will be counted only once using the most closely related event).

Additionally, subjects reporting TEAEs will be summarised for SOC and PT by closest relationship to IMP (i.e., unrelated, possibly related or related). Counts will be given for total number of subjects, not for events. Counts by closest relationship will be given (i.e., subjects experiencing more than 1 TEAE will be counted only once within each SOC and PT using the most closely related event).

11.2.1.5 Summary of Adverse Drug Reactions (ADRs)

All subjects reporting ADRs will be summarised. Counts will be given for number of subjects and number of events. Subjects experiencing more than 1 ADR will be counted only once for number of subjects but will be counted more than once for number of events.

Additionally, subjects reporting ADRs will be summarised for SOC and PT. Counts will be given for number of subjects and number of events. Subjects experiencing more than 1 episode of an ADR will be counted only once within each SOC and PT.

11.2.1.6 Summary of Serious Adverse Events

All subjects reporting treatment -emergent serious AEs (SAEs) will be summarised. Counts will be given for number of subjects and number of events. Subjects experiencing more than 1 SAE will be counted only once for number of subjects but will be counted more than once for number of events.

Additionally, subjects reporting treatment -emergent SAEs will be summarised for SOC and PT. Counts will be given for number of subjects and number of events. Subjects experiencing more than 1 episode of a SAE will be counted only once within each SOC and PT.

11.2.2 Listings for Adverse Events

All pre-dose AEs (as defined in Section 11.2) will be listed including SOC and PT.

A separate data listing of all TEAEs will be provided including the SOC and PT. In addition, a listing of all SAEs will be provided.

11.3 Laboratory Evaluations

The details of sample collection for laboratory safety analysis are described in the study protocol.

Where a value is provided by the safety laboratory as either above or below the limit of detection (LOD) this will be set to the respective LOD itself for descriptive summaries. No imputations will be made in the individual listings.

